## 3. Procedures

a) Describe in chronological order of event(s) how the activities will be conducted, providing information about all procedures (e.g. interventions/interactions with subjects, data collection, photographing, audio and video recording), including follow up procedures.

Potential participants will be identified at their office visits to the University Women's Health Specialists either at Kapi'olani or Queen's. If a patient desires surgical termination of a first trimester pregnancy or management of a failed pregnancy in the first trimester, they will first receive standard counseling and provide informed consent for the procedure. Next, the patient's eligibility for our study will be assessed. If the patient is eligible, she will be asked by a member of the research team if she is interested in participating. If she is, the study will be explained to her and written consent will be obtained after she is given the opportunity to have all of her questions answered. The patient will then complete a written questionnaire to collect demographic data.

This prospective randomized control trial will consist of two study arms. As participants are enrolled they will be randomly assigned to Arm 1, where a paracervical block will be administered with 20 cc of 1% lidocaine, which is our standard office protocol, or to Arm 2, where a paracervical block will be administered with 20 cc of 1% lidocaine buffered with 8.4% sodium bicarbonate. Patients will be randomly assigned to either Arm 1 or Arm 2 of the study. Prior to the start of the study, study assignments will be generated in a 1:1 ratio. A statistician not involved with the conduct of the study will use a computer random number generator to generate random permuted blocks. The random permuted blocks will also be randomly varied in sizes of 4, 6, & 8. This statistician will place allocation assignment cards in sequentially numbered, sealed, opaque envelopes. A different randomization scheme will be used for each location, one at the Kapi'olani office and one at the Queen's office.

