A clinic staff member not involved with the conduct of the study will be trained specifically in the opening of the allocation envelopes. The clinic staff member will be trained to pull envelopes individually in a sequentially numbered order. The staff member will be trained to open the envelope and remove the study card to read the allocation group: buffered lidocaine or plain lidocaine. The staff member will be trained to not tell anyone involved in the study of the allocation assignment. The clinic staff member will then draw up the buffered lidocaine or plain lidocaine in an unlabeled syringe, and give it to the procedural physician or surgical assistant for study administration.

**Protocol Title:** Buffered Lidocaine for Paracervical Block to Decrease Injection Pain During First Trimester Surgical Abortions

**Protocol Type:** Unified IRB Form

**Date Submitted:** 01/30/2017

**Approval Period:** Draft

**Important Note:** This Print View may not reflect all comments and contingencies for approval. Please check the comments section of the online protocol. Questions that appear to not have been answered may not have been required for this submission. Please see the system application for more details.

---

All patients who consent to the study will receive standard counseling prior to their procedure. The procedure will start with a bimanual exam by the provider. Next, the provider will place a speculum, cleanse the cervix with betadine solution, and place a single-tooth tenaculum on the anterior lip of the cervix. At this point, participants assigned to Arm 1 will receive a paracervical block loaded with 20 cc of 1% lidocaine with 10 cc injected at the 4 and 8 o'clock positions of the cervicovaginal junction. Participants assigned to Arm 2 will receive a paracervical block loaded with 18 cc of 1% lidocaine and 2 cc of 8.4% sodium bicarbonate in the same fashion. The research assistant will ask the patient to verbally report their level of pain based on the 100 mm visual analog scale at the following points of the procedure:

- 1) Prior to the start of the procedure (baseline)
- 2) After speculum placement
- 3) After paracervical block
- 4) After cervical dilation
- 5) After suction curettage
- 6) Fifteen minutes postoperatively

i) Be sure to identify what procedures are experimental and what are standard of care or established practice for the condition/situation.

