Based on previous research showing that a clinically relevant decrease in pain on a 100 mm VAS is at least 15 mm, we need to enroll 88 patients (44 in each group) to show this difference with 80% power and alpha of 0.05. Inflating this number by 10% to account for potential dropout (which is unlikely due to the lack of longitudinal follow-up), we obtain a total sample size of 98 patients (49 in each group).

Based on the typical volume of patients seen in our office practice, we anticipate that enrollment will take approximately 6-8 months.

We will assess the primary objective by comparing the mean pain score after paracervical block from participants receiving buffered

**Protocol Title:** Buffered Lidocaine for Paracervical Block to Decrease Injection Pain During First Trimester Surgical Abortions

**Protocol Type:** Unified IRB Form

**Date Submitted:** 01/30/2017

**Approval Period:** Draft

**Important Note:** This Print View may not reflect all comments and contingencies for approval. Please check the comments section of the online protocol. Questions that appear to not have been answered may not have been required for this submission. Please see the system application for more details.

---

We will assess the primary objective by comparing the mean pain score after paracervical block from participants receiving buffered lidocaine versus the mean pain score after paracervical block from participants receiving plain lidocaine. To assess our secondary objectives, we will compare the mean pain score after cervical dilation between participants assigned to Arm 1 and Arm 2 as well as compare postoperative pain between the two arms. All analyses will assume a statistical significance level of 0.05. In addition, we will monitor the extra costs of preparing buffered lidocaine solutions and how the preparation of buffered lidocaine impacts clinic flow and staffing.

c. Alternative Procedures. Describe any alternatives to participating in the research. (e.g., standard of care treatment, etc.). Any standard treatment that is being withheld must be disclosed. This information must be included in the consent form.

If a participant decides to withdraw from the study, she will receive our standard of care which is to administer a paracervical block using 20 cc of 1% plain lidocaine prior to the procedure.

d. Will subjects be followed after their active participation is complete?

N

If yes, explain why and describe how:

---

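### Does wording the primary comparison by solution received, with the dilation comparison worded by assigned arm, commit the trial to an as-treated primary analysis?

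*Combined protocol and SAP*

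**What the plan says.** Section 4b of the combined protocol and SAP describes three comparisons in two consecutive sentences, and each names its groups differently.

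- Primary, pain after the block: means are compared "from participants receiving buffered lidocaine versus the mean pain score after paracervical block from participants receiving plain lidocaine".
- Secondary, pain after dilation: "we will compare the mean pain score after cervical dilation between participants assigned to Arm 1 and Arm 2".
- Secondary, postoperative pain: "as well as compare postoperative pain between the two arms".

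The available text does not mention intention to treat, per protocol, as treated or any other analysis set. Section 16 lists a separate protocol file that is not part of the material, so it cannot be said that a definition is missing from the trial's papers as a whole.

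Three other statements bear on whether assigned and received solution can differ. Section 3a places randomization at enrollment ("As participants are enrolled they will be randomly assigned to Arm 1"). It then has a staff member outside the study read the card and "draw up the buffered lidocaine or plain lidocaine in an unlabeled syringe". Section 4c covers withdrawal: "If a participant decides to withdraw from the study, she will receive our standard of care", which is plain lidocaine whatever the assigned arm.

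**The concern.** In a superiority trial the primary comparison is normally made by assigned arm, because only that grouping keeps the balance that randomization gives. Here the primary endpoint has the wording that, read literally, groups by treatment received, while a secondary endpoint in the next sentence has the randomized wording. A reader could take the contrast as deliberate.

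On that reading, a participant assigned to the buffered arm who was given plain lidocaine and then scored would count in the plain group. If such participants tended to feel more pain, their move would raise the plain mean, remove high scores from the buffered group, and suggest a benefit that is not there. With no analysis set written down, the grouping could also be chosen after the scores are known. Assignment comes before the block and the syringe is unlabeled, so a mismatch cannot be ruled out.

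**Working it through.** **1. What the wording means.** Section 3a says "participants assigned to Arm 1 will receive a paracervical block loaded with 20 cc of 1% lidocaine" and describes Arm 2 in parallel terms, so assignment and receipt are treated there as one thing. Section 9 (Benefits) likewise refers to those who receive the buffered solution when it means the buffered arm. In Section 4b the labels pass from solution received, to assigned arm, to the two arms, with no sign that the grouping is meant to change. The natural reading is that all three name the randomized groups.

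**2. Can a scored participant move between groups?** Bias under the null needs someone who got the other solution, was scored after the block, and was selected in a way related to pain.

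- *Withdrawal before the block.* She leaves the study and probably gives no post-block score. That is missing data, not a change of group.
- *Drawing-up error.* The staff member works from a card in a sealed envelope and prepares the syringe before the injection, so the error precedes the score. Nothing in the documents ties it to how much pain the patient will report.

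Neither route meets all three conditions.

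**3. Size if a pain-related mismatch is simply assumed.**

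Inputs: n = 49 per arm (Section 4b). SD = 25 mm is an assumption, since no SD is stated. It is close to the 24.8 mm implied by 44 per group, 15 mm, 80% power and 0.05 under a two-sided two-sample t-test. The gap g = 10 or 20 mm is an assumption with no source in the documents. k is the number of scored Arm 2 participants given plain lidocaine. Arm 1 is taken to hold the same number of such patients, and there is no true treatment effect.

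Grouped by receipt, the plain group has n + k members, of whom 2k score g higher, and the buffered group has n − k members, none of them high scorers:

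- spurious difference = −2kg/(n + k)
- k = 1: −2 × 10/50 = −0.40 mm and −2 × 20/50 = −0.80 mm
- k = 2: −4 × 10/51 = −0.78 mm and −4 × 20/51 = −1.57 mm
- SE at k = 1: 25 × √(1/50 + 1/48) = 5.05 mm

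Two-sided rejection rate at nominal 0.05, with SD 25 mm and g = 20 mm:

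| Scored mismatches | By receipt, normal approximation | By receipt, simulated t-test | By assignment, simulated t-test |
|---|---|---|---|
| 1 | 5.3% | 5.1% | 4.8% |
| 2 | 6.1% | 5.8% | 4.7% |
| 5 | 11.3% | 10.3% | 4.4% |

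The simulated values are the ones to use, because the approximation leaves out the variance that the shifted patients add. With g = 0, meaning mismatches unrelated to pain, the by-receipt rate is 5.0% for every k.

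**4. The other side of the choice.** Grouping by assignment dilutes a true 15 mm effect by 15k/49: 0.31 mm for one mismatch (leaving 14.7 mm) and 0.61 mm for two (leaving 14.4 mm). That is also small.

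**The case for a change.** The strongest case for acting is that the inconsistency is real, concerns the only primary comparison, and could be removed by changing one word. Grouping by assigned arm is protected by randomization whatever happens in the preparation room, while grouping by receipt is sound only if nothing goes wrong. The plan describes no check of the syringe contents and allows 10% for dropout, though it calls dropout unlikely. Leaving the grouping open also leaves room for a choice after the scores are seen.

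What stands is that the three phrases differ and that the available text defines no analysis set. What does not stand is the step from there to a threatened result. The freedom to choose matters only if the two groupings give different answers, and without scored mismatches they are the same. The dropout allowance concerns missing scores, which neither wording addresses. Reaching a type I error near 10% takes five scored mismatches out of 49, all in patients with markedly higher pain, and nothing in the plan predicts this.

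**Conclusion.** The concern does not call for a change. The varied wording is loose drafting: receiving a solution is best read as an arm label, and an analyst working from Section 4b would compare the two randomized groups for all three endpoints. The trial has one injection at one visit and is scored directly after the block, so there is little opportunity for assigned and received solution to part company, and the documents give no pain-related reason for them to do so.

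The expected effect on bias and type I error is essentially nil. It is exactly zero if there are no mismatches, and zero under the null if mismatches are unrelated to pain. The hypothetical figures of about 5.1% and 5.8% for one and two mismatches rest on an assumed SD of 25 mm and an assumed 20 mm gap that has no mechanism in the plan.

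Two assumptions support this conclusion: that a participant who withdraws before the block gives no score, and that drawing-up errors are unrelated to pain. The separate protocol file may define the analysis set, but the conclusion does not depend on it.

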**\* \* \* Background and additional procedures \* \* \***

**4. Background and additional procedures**

**a. Relevant Background: Discuss the present knowledge, appropriate literature and rationale for conducting the research. Include the rationale for the selected subject population.**

A small number of studies have addressed this research question with conflicting results.

A multiphase study was published in 1995 using various techniques of the paracervical block for surgical abortions. Using a 10 cm visual analog scale (VAS), the study found a statistically significant decrease in injection pain when using buffered lidocaine as compared to plain lidocaine and bupivacaine. However, the pain immediately after the injection decreased from 3 cm to 2 cm on the 10 cm VAS, which may not be a clinically relevant difference. Several pain studies have found that a 30% or 13-20mm difference on a 100mm VAS is clinically meaningful for patients.

Another study compared buffered lidocaine versus plain lidocaine for paracervical blocks for surgical abortions. Using an 11 point scale, the investigators found an 8% decrease in pain from injection when using buffered lidocaine versus plain lidocaine. Although this difference was statistically significant, the author concluded that this was most likely not clinically significant and thus not worth the extra cost of preparing the buffered solution.

Buffered lidocaine versus plain has been looked at in non-gynecological procedures as well. One randomized controlled study compared buffered lidocaine versus plain lidocaine for patients undergoing bilateral periocular surgery. Investigators found a 51% decrease in injection pain when using buffered lidocaine versus plain lidocaine, which was both statistically and clinically significant.

Another study compared 1% lidocaine with epinephrine versus 1% lidocaine buffered with 8.4% sodium bicarbonate for patients undergoing loop electrosurgical excision procedure (LEEP) procedure. Using a 100 mm Likert scale, the study found an eight-point decrease in procedural pain when using buffered lidocaine; however, this was not statistically significant.

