Loma Linda University conducted a study comparing pain using 1% lidocaine with epinephrine versus 1% lidocaine with epinephrine buffered with 8.4% sodium bicarbonate for patients undergoing eyelid surgery. Using a 10 cm visual analog scale, investigators found a trend toward decreased pain from injection when using buffered lidocaine; however, this was not statistically significant.

Two studies found no difference when using buffered lidocaine versus plain lidocaine. A dental study comparing buffered lidocaine versus plain lidocaine for maxillary injections found no difference in pain with 5% buffered, 10% buffered, and nonbuffered lidocaine. Another study compared buffered versus plain lidocaine for patients undergoing incision and drainage for pulpal necrosis. No significant difference in pain was found.

Thus, very few studies have specifically looked at buffered lidocaine versus plain lidocaine for paracervical blocks during first trimester surgical abortions. The studies that have been conducted have conflicting results. Some have found benefit by reducing pain from injection or procedural pain. Other studies have found no difference in pain.

It is important to determine the ideal anesthesia for first trimester surgical abortions since it is one of the most common outpatient procedures worldwide. Buffered lidocaine for paracervical injections may have benefit for patients. However, it is more expensive to prepare and requires more planning due to a shorter shelf life. Thus, buffered lidocaine should only be used if there is a definite benefit. It is therefore important to determine if buffered lidocaine decreases injection pain during paracervical blocks for first trimester surgical abortions.

We have decided to select our study population from patients at University Women's Health Specialists offices due to the high volume of patients seeking surgical terminations of pregnancy or surgical management of miscarriages. We believe our selected patient population will reflect the diversity of Hawai'i.

**b. Describe the statistical methods of the research and plans for analysis of the data (i.e. planned statistics, justification of sample size, etc.).**

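### Does planning only a 0.05-level comparison of means, with 15 mm used for sizing alone, leave the trial unable to answer its own question?

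*Combined protocol and SAP*

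**What the plan says.** Section 4b (statistical methods) plans to compare mean pain scores after the paracervical block between arms. Dilation and postoperative pain are the secondary comparisons. The only criterion it gives is "All analyses will assume a statistical significance level of 0.05". It names no confidence interval and no threshold for interpretation. The sample size rests on the premise that "a clinically relevant decrease in pain on a 100 mm VAS is at least 15 mm", from which "we need to enroll 88 patients (44 in each group) to show this difference" "with 80% power and alpha of 0.05". This becomes 98 (49 per group) after a 10% allowance for dropout. The same section also plans to track the extra cost of buffering and its effect on clinic flow and staffing.

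Section 4a (background) describes an earlier trial with a statistically significant result in which pain "decreased from 3 cm to 2 cm on the 10 cm VAS, which may not be a clinically relevant difference". It then reports that several pain studies found that "a 30% or 13-20mm difference on a 100mm VAS is clinically meaningful for patients". It ends by saying that "buffered lidocaine should only be used if there is a definite benefit", because buffering costs more and takes more planning.

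Section 2b gives the primary objective: whether buffering lowers injection pain compared with plain lidocaine.

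**The concern.** The background discounts an earlier significant result as possibly too small to matter and asks for a definite benefit before buffering is adopted. The analysis plan then offers only a test against zero. Taken literally, two awkward readings are possible. A difference of 10 to 15 mm could be significant and be presented as a benefit, although it is below the figure on which the trial is sized. A difference of 5 to 10 mm could be non-significant and be read as no benefit, although the interval still reaches 15 mm.

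The background also seems to hold two incompatible standards of relevance. A fall from 3 cm to 2 cm meets the relative criterion but not the absolute one, so a 10 mm result could be called relevant or irrelevant after the data are seen. At stake would be how the primary result is interpreted. The validity of the comparison itself is not in question.

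**Working it through.** **Inputs.** From section 4b: planning difference 15 mm, power 80%, alpha 0.05, 44 per group evaluable, 49 per group enrolled. From section 3: "study assignments will be generated in a 1:1 ratio". Not stated: SD and sidedness. I assume a two-sided test, derive the SD from the stated size, and show 20 to 30 mm as a range.

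**1. The plan's sample size.** Solving the two-mean formula for the SD:

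SD = 15 × √(44/2) / (1.960 + 0.842) = 15 × 4.690 / 2.802 = 25.1 mm.

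Forward with SD 25: n = 2 × (2.802 × 25/15)² = 43.6, so 44 per group. With the t-test, an SD of 24.8 mm gives 44. The dropout step reproduces: 88/0.9 = 97.8, so 98. The 88 is thus consistent with an SD of about 25 mm but cannot be confirmed from stated inputs.

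**2. Smallest observed difference that is significant** = t × SD × √(2/n), with SD 24.8:

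- 49 per arm: 1.985 × 24.8 × √(2/49) = 1.985 × 5.01 = 9.95 mm.
- 44 per arm: 1.988 × 24.8 × √(2/44) = 1.988 × 5.29 = 10.5 mm.
- SD 20 to 30: 8.0 to 12.0 mm at 49 per arm, 8.5 to 12.7 mm at 44.

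An observed difference of exactly 10 mm is borderline:

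| SD | 44 per arm | 49 per arm |
|---|---|---|
| 24.8 mm | p = 0.062 | p = 0.049 |
| 25 mm | p = 0.064 | p = 0.051 |

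**3. Is this peculiar to this trial?** If the SD equals its planning value, it cancels. At the planned n, the threshold as a fraction of the planning difference is 1.960/(1.960 + 0.842) = 0.70, and 0.70 × 15 = 10.5 mm. At 49 per arm, 10.5 × √(44/49) = 9.9 mm. A one-sided 0.05 test gives 1.645/(1.645 + 0.842) × 15 = 9.9 mm at 44 per arm and 9.4 mm at 49. The 70% figure holds for every two-sided superiority trial planned at 80% power and 0.05.

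**4. How often would the awkward readings arise?** Take a true effect of 10 mm, SD 24.8 and 49 per arm, so SE = 5.01 mm:

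- significant: P(observed > 9.95) = 0.50;
- significant with an estimate under 15 mm: P(9.95 < observed < 15) = 0.35;
- non-significant with an interval that still includes 15 mm: P(5.05 < observed < 9.95) = 0.33.

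**5. What would a fixed rule gain?** Suppose clinical relevance is declared when the interval excludes 0 and the estimate is at least 15 mm.

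- An estimate of exactly 15 mm has an interval of 15 ± 9.95, about 5 to 25 mm, so values the protocol doubts are not excluded.
- A true 15 mm effect meets the rule about 50% of the time. An 80% chance needs a true effect of 15 + 0.842 × 5.01 = 19.2 mm.
- At a true 10 mm, the two groups in step 4 (0.35 + 0.33 = 0.68) stay ambiguous under new labels.

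**6. The two relevance figures.** A fall from 30 mm to 20 mm is 10/30 = 33%, above 30%, but 10 mm is below 13 mm. The criteria do disagree here: 30% equals 15 mm only when the comparator mean is 50 mm. However, both figures are a report of other studies in the background. Section 4b carries forward one number, 15 mm, so the analysis plan contains no relative criterion to conflict with it.

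**The case for a change.** The strongest case for a change uses the protocol's own standard. It doubts a significant 10 mm result and wants a definite benefit, yet nothing commits it to reading its own result against 15 mm. For every SD from 20 to 30 mm the significance threshold lies below 13 mm, the low end of the absolute range it cites, so the point does not depend on the assumed SD. A reading fixed in advance is stronger than one chosen later, and the cost is a few words.

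Part of this stands. Section 4b names neither a confidence interval nor a reference value for interpretation, and the arithmetic is right.

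The rest does not carry. The plan never says that p below 0.05 settles whether buffering should be used. It states a test level, and it also gathers cost and workflow information. Predicting that a 10 to 15 mm result would be presented as a clinical benefit runs against section 4a, where the investigators make the opposite judgment about someone else's significant result. The objective in section 2b asks whether pain falls, and a comparison of means answers that. The definite benefit in section 4a is not defined there as 15 mm. Section 16 also lists a separate protocol file that is not among the documents, so whether it says more on interpretation is unknown.

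**Conclusion.** No change to the plan is needed. The missing interval and reading are detail that an analyst fills in the ordinary way: report the mean difference with its 95% confidence interval and discuss it against 0 and against the 15 mm on which the trial was sized. That uses the same data and the same test.

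The gap between the significance threshold (about 10 to 10.5 mm) and the planning difference (15 mm) is a property of conventional 80%-power designs and not an error here. The mismatch between the relative and absolute relevance figures is loose background wording with no role in the analysis. A prespecified point-estimate rule is a trade-off without clear gain: it alters no estimate or test, a true 15 mm effect meets it only about half the time, and about two-thirds of results at a true 10 mm stay ambiguous.

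These figures rest on a two-sided test and an SD of about 25 mm implied by the stated size and power. Across SDs of 20 to 30 mm the threshold moves between 8.0 and 12.7 mm, which does not alter the conclusion.
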